7.6 Height, Weight, Body Mass Index

Body weight and height are to be measured at Screening. Body weight will be repeated at the visit at the end of each Period as specified in the Schedule of Assessments. Participants will wear indoor

clothing and remove their shoes prior to the measurements. Body Mass Index (BMI) will be calculated and recorded.

7.7 Vital Signs

Vital signs (pulse rate, blood pressure, respiration rate, and temperature) will be measured at Screening, during the Treatment Visits, and Follow-Up as specified in the Schedule of Assessments. Blood pressure and heart rate will be measured using a calibrated, fully automated machine with a cuff that is appropriate to the size of the upper arm. If a fully automated machine is not available, blood pressure may be measured manually. For each participant, measurement on the same arm (right or left) using the same method (either automated or manual) should occur throughout the study. All blood pressure measurements should be obtained with the participant in the sitting position, after the participant is at rest for 5 minutes.

Additional vital signs measurements may be performed as deemed medically necessary by the Investigator.

7.8 Laboratory Assessments

Appendix 14.2 Clinical Laboratory Analytes provides a list of the clinical laboratory tests that will be performed according to the collection schedule provided in the Schedule of Assessments. Blood samples for chemistry and hematology and urine samples will be collected in accordance with acceptable laboratory procedures.

Since this is a single-site study, an accredited local laboratory will be used to analyze the clinical laboratory samples.

7.9 Management of Abnormal Clinical Laboratory Tests

It is the Investigator's responsibility to review the results of all lab tests as they become available and to document their review by signing and dating the lab report. For each lab test outside of the laboratory normal range, the Investigator must ascertain if this is a clinically significant change from baseline for the individual participant. This determination does not necessarily need to be made the first time an abnormal lab is observed. The Investigator may repeat the lab test or request additional tests to verify the results of the original lab test.

All clinically significant laboratory abnormalities occurring during the study that were not present at baseline should be followed and evaluated with additional tests if necessary, until determination of the underlying cause or adverse event resolution.

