This is a single-center, Phase 2, single-blind, 4-period sequential study will obtain a preliminary assessment of the effects of ergoloid mesylates (EM) 1 mg TID and 5-hydroxytryptophan (5-HTP) 100 mg TID and the combination compared to a placebo period in participants with Fragile X Syndrome. The study will consist of a Screening period of up to 28 days prior to initial study drug administration, followed by four 4 week single-blind treatment periods. The screening and baseline visits may occur at the same time, provided the results of safety labs can be obtained. A final follow-up visit or phone contact for safety is planned one week after the conclusion of Period 4.

Eligible participants will be started on EM for 4 weeks in Period 1, then will take EM and 5-HTP for 4 weeks in Period 2, then, 5-HTP for 4 weeks in Period 3, then placebo for 4 weeks in Period 4. Study visits will occur at baseline and every 4 weeks at transition times between periods, then at the end of the study.

Brief cognitive and behavioral assessments will be performed during each clinic visit. Safety and tolerability assessments will include adverse event monitoring, vital signs, blood chemistry and hematology, and urinalysis.

	4 Weeks Period 1	4 Weeks Period 2	4 Weeks Period 3	4 Weeks Period 4		
Screen/Enroll ───→	EM	EM + 5-HTP	5-HTP	Placebo		
N=15 participants						
EM=ergoloid mesylates 1 mg TID, 5-HTP = 5-hydroxytryptophan 100 mg TID						
Planned Numbers of Participants						
Enrollment of a total of 15 eligible participants is planned.						
Study Duration						
The total duration of the study for each participant will be up to 21 weeks, including a maximum of 4-week screening						

The total duration of the study for each participant will be up to 21 weeks, including a maximum of 4-week screening period, four 4-week Single-Blind treatment Periods, and a follow-up telephone call approximately 1 week after the last treatment visit.

Study Procedures:

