4 INVESTIGATIONAL PLAN

4.1 Overall Study Design

This is a single center, Phase 2, single-blind, 4 period study to obtain preliminary assessment of the effects of ergoloid mesylates (EM), 5-hydroxytryptophan (5-HTP), and the combination in participants with Fragile X Syndrome. As schematic display of the study design is shown in Figure 7.

The study will consist of a Screening period of up to 28 days prior to initial study drug administration, followed by four 4-week single-blind treatment periods. The screening and baseline visits may occur at the same time, provided the results of safety labs can be obtained. No washout period will be utilized between treatment periods. A final follow-up phone contact for safety is planned one week after the conclusion of Period 4.

Eligible participants will be started on over-encapsulated EM 1 mg TID during Period 1, then will take EM 1 mg TID and 5-HTP 100 mg TID in Period 2, then 5-HTP 100 mg TID in Period 3, and placebo in Period 4. Throughout all 4 periods, participants will take two identical capsules three times a day. If only taking one over-encapsulated drug, they will take one over-encapsulated placebo pill with the drug at each dose, and when in period 4 they will take two over-encapsulated placebo pills at each dose.

Cognitive and behavioral assessments will be performed during each clinic visit. Safety and tolerability assessments throughout the study will include adverse event monitoring, vital signs, blood chemistry, hematology, and urinalysis.

Figure 7 Study Design Schematic

N=15 participants

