6 TREATMENT OF PARTICIPANTS

6.1 Treatment Arms

In this single-blind, 4-period study, 15 participants will be enrolled and will be treated with the following during the 4 periods of the study.

- Ergoloid mesylates 1 mg TID (Medisca)* and matching placebo for 5-Hydroxytryptophan 100mg TID***
- Ergoloid mesylates 1 mg TID (Medisca) and 5-Hydroxytryptophan 100 mg TID (5-HTP, Basic Vitamins)**
- 5-Hydroxytryptophan 100 mg TID (5-HTP, Basic Vitamins) and matching placebo for Ergoloid mesylates 1mg TID***
- Matching placebo for Ergoloid mesylates 1mg TID and Matching placebo for 5-Hydroxytryptophan 100mg TID ***

* 1 mg will be mixed with methyl cellulose and placed in a size 00 capsule ** will be over-encapsulated in identical size 00 capsules ***will be ascorbic acid powder in identical size 00 capsules

All study medications will be prepared at the RUMC research pharmacy and provided as identicalappearing capsules in bottles. Two bottles of capsules will be provided at each visit and one capsule from each bottle will be taken 3 times a day. Doses should be taken at least 4 hours apart.

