Any medical condition already present prior to the participant taking the first dose of study drug should be reported in the medical history. Any SAEs occurring prior to the first dose of study drug should be reported as an update to medical history as well as an adverse event. Any pre-existing medical condition or signs or symptoms that changes in severity, frequency, or seriousness after the participant takes the first dose of study drug and through the Follow-up Visit should be reported as an adverse event.

Clinically significant abnormal laboratory values or other examinations (e.g., ECG) that are detected after the first dose of study drug and worsen during the study should be reported as adverse events. An abnormal laboratory result that is not verified by repeat testing does not necessitate reporting as an adverse event. The Investigator will exercise his or her medical, scientific, and clinical judgment in deciding whether an abnormal laboratory finding or other abnormal assessment is clinically significant. Clinically significant abnormal laboratory values occurring during the clinical study will be followed until repeat tests return to normal, stabilize, or are no longer clinically significant. Any abnormal test that is determined to be an error does not require reporting as an adverse event. Treatment of any adverse reactions will be evaluated and managed by a physician.

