14.1 Schedule of Assessments

	PERIOD 1		PERIOD 2 PERIOD 3			PERIOD 4						
	Screening Days -28 thru 0	P1 Day 1	P 1 Wk1 (±1)	P 1 Wk4 (±5)	P2 Wk5 (±1)	P2 Wk8 (±5)	P3 Wk9 (±1)	P3 Wk12 (±5)	P4 Wk13 (±1)	P4 Wk16 (±5)	P4 Wk16 (ET ^a) (±5)	P4 Wk17 (±1)
Clinic Visit	X	Х		Х		Χ		Χ		Х	Х	
Telephone Call			Х		X		Х		Х			X
Informed Consent	Χ											
Eligibility	Χ	Xb										
Medical /Surgical History	X											
Demographics	Χ											
Physical Exam	Х											
Abbreviated PE		Xb		Х		Χ		Χ		Х	Х	
Ht, Wt, BMI	Х			X ^c		Xc		Xc		Xc	Xc	
Vital Signs ^d	Х	Xb		Х		Χ		Χ		Х	Х	
Chemistry and Hematology	X			X		X		X		X	X	
Urinalysis	Х			Х		Х		Χ		Х	Х	
Suicidality	Х			Х		Х		Χ		Х		Χ
Dispense Study Medication		X		X		X		X				
1st Dose of Medication		X										
Stanford-Binet	Х											
NIH-TCB		Χ		Χ		Χ		Χ		Х	Х	
KiTAP		Х		Х		Х		Χ		Х	Х	
CGI-S		Х		Х		Х		Х		X	X	
CGI-I				Х		Χ		Χ		Х	Х	
VAS		Χ		Х		Χ		Χ		Х	Х	
ABC		Χ		Х		Χ		Χ		Х	Х	
ADAMS		Χ		Х		Χ		Χ		Х	Х	
Vineland-3		Χ		Х		Χ		Χ		Х	Х	
ERP		Χ		Х		Χ		Χ		Х	Х	
Eye Tracking		Χ		Х		Χ		Χ		Х	Х	
IP accountability				Χ		Χ		Χ		Χ	Χ	
Con Meds	Χ	Xb	X	Χ	Χ	Χ	X	Χ	Χ	Χ	Χ	X
Adverse Events		Χ	X	Χ	Χ	Χ	X	Χ	Χ	Χ	Χ	X
Final Disposition												Χ
						1		1	1		1	

**Note: Screening and Period 1 Day 1 visits may be combined* ^a If early termination occurs, the Week 16 procedures should be completed at the time of the participant's withdrawal (if possible)

^b Do not need to repeat if screening and baseline done at same visit

^cWeight only

^d Vital signs include pulse rate, blood pressure, respiration rate, and temperature

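### A laboratory abnormality first seen at Week 8 or Week 12 can clear because the drug was stopped, and the repeat-test rule in Section 8.1 then lets it go unreported for that regimen

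*Combined protocol and SAP*

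**What the plan says.** Section 7.9 requires the investigator to decide, for every value outside the normal range, whether it is a clinically significant change for that participant. It sets no deadline: "This determination does not necessarily need to be made the first time an abnormal lab is observed". It continues: "The Investigator may repeat the lab test or request additional tests to verify the results of the original lab test". The repeat is optional, and nothing is said about when it is taken or on which regimen.

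Section 8.1 supplies the consequence: "An abnormal laboratory result that is not verified by repeat testing does not necessitate reporting as an adverse event". The wording is permissive.

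The timing comes from the design:

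- The Synopsis (Study Design) states: "Study visits will occur at baseline and every 4 weeks at transition times between periods, then at the end of the study".
- Section 4.1 gives the order EM, EM + 5-HTP, 5-HTP, placebo, and adds: "No washout period will be utilized between treatment periods".
- In the Schedule (14.1), the row "Chemistry and Hematology" is marked at Screening, Weeks 4, 8, 12 and 16, and early termination. Urinalysis follows the same pattern. The row "Dispense Study Medication" is marked at Day 1 and Weeks 4, 8 and 12.
- Section 6.1 says of supply: "Two bottles of capsules will be provided at each visit".
- The contacts one week into each period and at Week 17 are telephone calls without samples.

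The Synopsis (Safety Analyses) counts clinically meaningful laboratory findings among the adverse events and tabulates those separately for placebo and the three active regimens. Section 10.5 also summarises laboratory values and their changes from baseline.

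**The concern.** A normal repeat has two possible explanations. Either the first value was a chance or laboratory artefact, or it was a real drug effect that ended when the drug was stopped. Where treatment continues unchanged, the first explanation is the natural one. Here the sample is drawn at the visit where the regimen changes, so the second is open too, and it points the opposite way: return to normal after withdrawal is evidence for the drug as cause. The repeat-test rule in 8.1 makes no distinction between the two.

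Safety and tolerability of EM, 5-HTP and the combination is a stated objective (3.4.1). If reversible abnormalities can drop out after some draws and not others, the comparison between regimens can be distorted as well as the individual counts. The discretion lies with an investigator who knows the treatment (6.4), which is a further reason for a fixed recording rule.

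**Working it through.** The plan states no figure on this point, so there is none to reproduce. The check sets each on-treatment draw against the regimen dispensed at the same visit (regimen order from 4.1, draws and dispensing from 14.1).

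| Draw | Regimen at draw | Dispensed next | Withdrawn | Kept |
|---|---|---|---|---|
| Week 4 | EM | EM + 5-HTP | none | EM |
| Week 8 | EM + 5-HTP | 5-HTP | EM | 5-HTP |
| Week 12 | 5-HTP | placebo | 5-HTP | none |
| Week 16 | placebo | nothing | none | none |

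1. **Does the regimen change?** Yes, after all three active-period draws.

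2. **Is the responsible drug withdrawn?** Only sometimes. There are four pairs of drug and draw: EM at Weeks 4 and 8, and 5-HTP at Weeks 8 and 12. The drug is kept in 2 (EM after Week 4, 5-HTP after Week 8) and withdrawn in 2 (EM after Week 8, 5-HTP after Week 12). With 15 participants and no dropout, a component is withdrawn after 2 × 15 = 30 of 3 × 15 = 45 active-period draws.

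3. **Which effects can be lost?** An EM effect visible at Week 4 can be confirmed at Week 8 because EM continues. A 5-HTP effect visible at Week 8 can be confirmed at Week 12. What is exposed is a reversible effect first seen at the last draw on the drug: EM or the combination at Week 8, and 5-HTP at Week 12.

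4. **When would a repeat fall?** The next scheduled draw is 28 days later. Reading the ±5 windows as days, the gap runs from 28 − 10 = 18 to 28 + 10 = 38 days, always on a different regimen. An unscheduled repeat could come sooner. Whether it precedes the first dose of the new regimen depends on laboratory turnaround and first-dose timing in Periods 2 to 4, neither of which is stated. Section 7.10 asks that additional testing to assess an event be discussed first with the sponsor unless urgent, which makes an immediate repeat somewhat less likely.

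5. **What does one lost event do?** With all 15 participants assessed in a period, each participant whose event goes unreported lowers that regimen's incidence by 1/15 = 6.7 percentage points. Dropouts are not replaced (5.5), so the step is larger with fewer participants. How many would be lost cannot be derived: the documents give no rate of abnormalities, of reversibility or of deferral.

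**The case against.** The strongest reply is that existing text already covers much of this.

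- Section 8.1 follows significant values until repeats normalise or stabilise, so normalisation is treated as resolution.
- Section 8.3.1 directs attention to the timing of exposure, and the investigator knows the regimen.
- Section 10.5 keeps every abnormal value in the laboratory summaries.
- A local laboratory is used (7.8), and screening and baseline may be combined if safety results can be obtained, so rapid results are contemplated. Nothing forbids a repeat before the switch.
- The study is exploratory and its analyses are descriptive.

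Part of this stands. An attentive investigator could recognise resolution on withdrawal, and a prompt repeat would avoid the problem. But the follow-up rule applies once a value has been judged significant, and 7.9 allows that judgement to wait for the repeat. The causality factors in 8.3.1 do not list resolution after stopping, and a result left unreported under 8.1 need not reach causality assessment at all. The laboratory summaries give means, medians and ranges, not significance or relatedness, so they do not replace the by-regimen event table.

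A reader might also infer more than the documents support:

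- *That every transition visit loses drug effects.* EM continues after Week 4 and 5-HTP after Week 8, and Week 16 follows placebo.
- *That the plan deletes these events.* The repeat is optional and the 8.1 wording only relieves the investigator of a duty to report.
- *That 7.9 itself treats a normal repeat as failure to verify.* That consequence comes from 8.1.
- *That persisting abnormalities are assigned to the regimen in force when the decision is made.* No text does this. The only dating item listed is date of onset, under serious adverse event documentation (8.3.3).

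**Conclusion.** The concern holds in a limited form. Sections 7.9 and 8.1 together allow a reversible EM or combination abnormality first seen at Week 8, or a 5-HTP abnormality first seen at Week 12, to clear after the drug is withdrawn and go unreported as an adverse event for the regimen that caused it. At Week 4 the risk is only that an EM effect confirmed during Period 2 is attributed to EM + 5-HTP, because the documents do not say which regimen a laboratory finding belongs to. Week 16 is not affected.

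This rests on two assumptions: that the repeat is drawn after the new regimen starts, and that the investigator uses the option not to report. The loss is therefore possible, not automatic, and the documents support no estimate of its size beyond the 6.7-point step per missed participant. It bears on the safety comparison between regimens, not on the efficacy summaries. It deserves correction because the gap is in a stated rule and closing it takes little.

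**What to change.** Keep the option to defer the decision and repeat the test. Add the following to the repeat-testing sentence in 8.1, with a cross-reference in 7.9:

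> A normal repeat drawn after the regimen has changed does not count as failure to verify. The original result is assessed for clinical significance on its own, attributed to the regimen being taken when the sample was drawn, and, if clinically significant, recorded as an adverse event that resolved after the change of regimen.

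The attribution clause also settles Week 4. No visit, sample or treatment changes, and a confirmatory repeat on the same regimen keeps its present role, as does the existing exemption for tests found to be in error.

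The cost is some additional laboratory events that may be chance findings. For scale, Appendix 14.2 lists 14 chemistry and 13 hematology analytes (counting the five differential cells), or 27. Over three transition visits and 15 participants that is 27 × 3 × 15 = 1,215 results. If a fraction f fell outside range by chance, 1,215 × f would do so, or about 61 at f = 0.05 (an assumed value). Section 7.9 already requires a significance decision on each, and only those judged significant would become events, so the increase should be far smaller than 61. At Week 4, where EM continues, a normal repeat is fair evidence against an EM effect, and the investigator can weigh that when rating relatedness under 8.3.1.

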7.10 Additional Safety Measures

Participants and caregivers will be instructed to inform the study physician and/or research personnel of any AEs, including significant behavioral changes not within the typical variation for the participant, that occur at any time during the study.

Procedures will be completed as specified in this protocol unless contraindicated due to a reported AE.

If, in the judgement of the Investigator, additional testing is required to assess an adverse event or otherwise clinically significant event, this testing should be discussed first with the sponsor unless needed urgently.

7.11 Exploratory Efficacy Assessments

7.11.1 Descriptions of Efficacy Assessment Instruments

Several assessment tools for cognitive and behavioral measures will be utilized in this exploratory study. Raw scores (not standardized) will be collected for all assessments, except for the Vineland -3 composites where age-equivalent scores will also be collected.

7.11.1.1 NIH-TCB

The NIH-TCB, a component of the NIH Toolbox for Assessment of Neurological and Behavioral Function, was developed by a team of more than 300 scientists from nearly 100 academic institutions as part of the NIH Blueprint for Neuroscience Research to standardize evaluations in specific clinical populations for investigations of neurological development and change, disease recovery, and therapeutic interventions.^{29,30,31} The NIH-TCB is a battery of extensively validated computer-administered cognitive tests with utility across childhood and adolescence, early adulthood, and old age. The NIH-TCB assessments were designed to minimize floor and ceiling effects which often are present in testing batteries designed for the general population. Downward extensions of many of the NIH-TCB tests have been created to allow feasibility down to a mental age of 3. Therefore, there is good reason to believe that the assessments are appropriate for individuals with intellectual disabilities. In fact, a pilot study has been published showing good feasibility and test-retest reliability in FXS and Down syndrome, and the instructions and testing protocol has been adjusted (without changing construct validity) for individuals with intellectual disabilities based on issues identified in the pilot study.³² Further validation of the adjusted measure was published subsequently.³³

The NIH-TCB includes 7 evaluations: Dimensional change card sort test (DCCS, measure of cognitive flexibility), Flanker inhibitory control and attention test (measure of inhibition and visual attention), Picture sequence memory test (measures episodic memory), List sorting working memory test (measures immediate recall and sequencing of different visually and orally presented stimuli), Pattern comparison test (measures processing speed), Oral reading recognition test (measures recognition of letters and words), Picture vocabulary test (measures receptive vocabulary).

7.11.1.2 Test of Attentional Performance (KiTAP)

The KiTAP is a computerized executive function battery that consists of eight nonverbal subtests measuring different basal as well as higher-order components of attention and executive functioning.³⁴ Each subtest can be assessed separately. Four subtests will be utilized in this study: alertness, distractibility, go-nogo, and flexibility. To ensure optimal motivation and compliance, all subtests are designed in the form of short games with an enchanted castle theme. The four subtests chosen for use in this study have been utilized in FXS populations and shown to be feasible, reproducible with evidence of clinical validity when scores are compared with standardized behavioral questionnaires addressing relevant functions. The KiTAP has shown evidence of response to pharmacological intervention in clinical trials of AFQ056 and metadoxine in FXS.^{35,36}

7.11.1.3 Clinical Global Impression

The CGI-I (and CGI-S) are gold standard global measures of severity and change with treatment in placebo-controlled pharmacotherapy trials in developmental disabilities and have been used extensively in prior clinical trials in FXS.^{37,38}

7.11.1.3.1 Clinical Global Impression Severity: Investigator Rated (CGI-S)

The Clinical Global Impression–Severity (CGI-S) is a global measure to provide a clinical judgment of a participant's overall condition based on a trained clinician's assessment of cognition, behavior and activities of daily living.³⁹ The assessment of severity will be made with a 7-point scale: 1, not ill; 2, very mild; 3, mild; 4, moderate; 5, marked; 6, severe; 7, extremely severe. The comparison will be made with respect to the overall experience of the clinician with individuals of the same age and sex.

